### **Power Analysis and Sample Size Requirement for Hypotheses 1 and 2**

Sample size was selected to permit analysis of the primary research questions at two-tailed alpha of .05 and power level of .80. Estimates of effect size follow Cohen (1988) and were conducted in G\*Power 3 (Faul et al., 2007). The primary analysis is the test of the strain X time interaction effects across repeated assessments of THC in the blood as well as assessments of working memory and the rewarding effects of the marijuana. To be conservative, we thus estimated an ICC of .60. Using a mixed model ANOVA design, with three groups, four assessment points, and an average ICC = .6 between assessment points, a total n=99 (33 per group) will allow us to detect an interaction effect as small as  $f=.12$ .

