### **Effects of THC Potency on THC Blood Levels, Working Memory, and Reward**

The first aim is designed to test whether the “potency” of marijuana in terms of THC level in the plant translates directly to THC levels in the blood. To test **Hypothesis 1**, those individuals who receive the high THC strain will demonstrate significantly greater blood THC levels, we will utilize random coefficient regression (RCR; Cohen et al., 2013) via SAS Proc Mixed. The between subjects factor will be strain (high THC versus medium THC versus low THC) and the within subjects factor is time (Time 1, Time 2, Time 3, Time 4). Blood level of THC is the dependent measure. The test of the strain X time interaction will indicate whether the pattern of effects is such that blood levels increase to a greater degree and remain higher across the course of the study in the strains with higher THC. Thus, we expect both a significant interaction as well as a main effect of strain. Assuming a significant omnibus test of the interaction, we will decompose the interaction

via planned posthoc contrasts in order to understand at which time points the three strains are different. At Appointment 1, Time 1 (baseline) we do not expect differences in THC since none of the participants will have switched strains. Appointment 2, Time 2 is the sober, before use at Time 3. Thereafter, we expect a difference in THC at Appointment 2, Time 3 in the high THC versus the medium and low THC groups, and that while all groups will decrease in THC over the course of the laboratory appointment between Time 3 and 4, the high THC group will continue to show higher blood levels than the medium THC group, and the medium THC group will show higher blood levels than the low THC group. Note that we will include a quadratic effect in the multilevel model both to appropriately model the quadratic effect and whether that quadratic trend differs by condition. It is important to note that since we are not directly controlling administration, and have instructed participants to ingest the marijuana ad libitum, that they themselves may moderate their consumption to achieve “desired” THC levels, as our pilot data suggest. Thus, those in the low and medium THC group may ingest more in order to match their typically desired level, and thus the groups might converge. In this case, it is possible that we may see fewer difference in blood levels of THC, or non-significant differences at some timepoints across groups.

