**Hypothesis 2** tests whether blood levels of THC are positively associated with diminished working memory and greater rewarding effects of the marijuana, operationalized with the DEQ. If analyses of Hypothesis 1 show that there are main effects by group suggesting that the higher THC strain results in significantly higher THC levels in the blood than the medium or low THC strains, the between-groups variable for models testing Hypothesis 2 will be group and we will include all four time points. Since participants were randomly assigned to group, this test allows for the highest internal validity in terms of causal conclusions about the effects of THC. If, on the other hand, participants titrate their own use such that there are few reliable between-groups differences, then actual blood levels of THC will become the between-groups (continuous) independent variable in tests of Hypothesis 2 and we will utilize timepoints 3-4 as the within-subjects effect of time. Our preliminary studies confirm wide variability in THC levels even among individuals using the same strain, so there will be adequate between-participant variability for these analyses. In either case, we will again use the RCR approach described above, and standard approaches to the estimation of interactions in regression (Aiken & West, 1991) in the case of a continuous IV (i.e., mean-centering prior to creation of the interaction term). In each model, the predictors will include the group variable (or continuous THC blood levels), a time variable, and their interaction.

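### Strain x time is the primary test for reward, but the DEQ is collected only at two post-use sessions, where that test cannot detect a constant strain difference

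*Protocol*

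**What the plan says.** All references are to the Protocol.

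- **Primary test.** The section on power analysis and sample size says "The primary analysis is the test of the strain X time interaction effects across repeated assessments of THC in the blood", and continues "as well as assessments of working memory and the rewarding effects of the marijuana". No other term is called primary.
- **Power.** "Sample size was selected to permit analysis of the primary research questions at two-tailed alpha of .05 and power level of .80". The calculation is for a mixed ANOVA "with three groups, four assessment points, and an average ICC = .6 between assessment points", and concludes that "a total n=99 (33 per group) will allow us to detect an interaction effect as small as" f=.12.
- **Hypothesis 2.** The section on effects of THC potency poses it as an association: higher blood THC goes with poorer working memory and greater reward, the latter measured by the DEQ.
- **Strain branch.** If the strains separate on blood THC, strain is the predictor and all four sessions enter the model.
- **Blood-THC fallback.** If participants titrate so that strains differ little, continuous blood THC replaces strain and "we will utilize timepoints 3-4 as the within-subjects effect of time".
- **Model terms, either branch.** "the predictors will include the group variable (or continuous THC blood levels), a time variable, and their interaction". The term that decides Hypothesis 2 is not named.
- **Schedule.** The instrument table in section XII (Procedures) lists the DEQ only under Sessions 3 and 4. The neurocognitive battery is listed under all four sessions. Both Sessions 3 and 4 follow use, and section XII puts them one hour apart.

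**The concern.** An interaction with time is a sound primary test when the model holds sessions before and after use: an acute effect is absent before, present after, and so appears as an interaction. That logic needs a pre-use measurement. The DEQ has none, so the model planned for reward in the strain branch cannot be fitted as described. What can be fitted has two post-use points, where the null of the named test is that the strain difference is equal at both. A real and stable difference in reward satisfies that null.

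At stake is the reading of Hypothesis 2 for reward. Taken literally, the plan could report no effect when strains differ clearly and steadily. A significant interaction would show only that the difference changed within the hour. If analysts turn to the main effect instead, they choose between two coefficients that the protocol has not ranked for this model. The blood-THC fallback leaves the same choice open for both reward and working memory.

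**Working it through.** **Inputs from the protocol.** N=99 (33 per group), k=3 groups, ICC ρ=.6, two-tailed alpha .05, f=.12, four assessments in the power calculation, DEQ at two.

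**Assumptions (the protocol gives no effect size for Hypothesis 2).** Steps of 0.3 to 0.5 SD between adjacent strains; THC-outcome correlation r of .2 to .5. The outcome has unit within-group variance at each session.

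**1. The stated figure reproduces.** λ = f²·N·m/(1−ρ) = 0.0144 × 99 × 4 / 0.4 = 14.256. With df = (3−1)(4−1) = 6 and (99−3)(4−1) = 288, power is .811. The smallest f with 80% power is .119.

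**2. It does not carry over to the DEQ.** With m=2, λ = 0.0144 × 99 × 2 / 0.4 = 7.128, df = 2 and 96, and power is .65. The smallest f with 80% power becomes .142. So even for an interaction, the stated sensitivity does not apply to reward.

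**3. What the interaction tests with two sessions.** Let D = Y4 − Y3 and A = (Y3 + Y4)/2. Strain x time is the one-way F test on D; the strain main effect is the one-way F test on A.

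- Var(D) = 2 × (1−.6) = .8 and Var(A) = .6 + .4/2 = .8.
- Strain means of −s, 0, +s at both sessions cancel in D, so its λ = 0 and it rejects at alpha whatever s is.
- For A, λ = 33 × 2s²/.8. With s=0.3 this is 7.425; with s=0.5 it is 20.625 (df 2 and 96).

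| Constant step between adjacent strains | Strain x time rejects (simulated) | Main effect, formula | Main effect, simulated (20,000 runs) |
|---|---|---|---|
| 0.3 SD | 5.1% | 67% | 68% |
| 0.5 SD | 4.9% | 99% | 99% |

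**4. If the strain difference fades.** Suppose the Session 4 step is half the Session 3 step. The step in D is then s/2 in size and the step in A is 0.75s.

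- s=0.3: λ for D = 33 × 2 × 0.15²/.8 = 1.856, power 21%; λ for A = 33 × 2 × 0.225²/.8 = 4.177, power 42%.
- s=0.5: λ for D = 33 × 2 × 0.25²/.8 = 5.156, power 50%; λ for A = 33 × 2 × 0.375²/.8 = 11.602, power 86%.

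**5. Blood-THC fallback, if the interaction is taken as deciding.** Slope b = r/√(1−r²), equal at both sessions, 20,000 simulated runs per row.

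| r | THC x time rejects | Averaged THC effect rejects |
|---|---|---|
| .2 | 4.9% | 62% |
| .3 | 4.9% | 93% |
| .4 | 5.1% | 99.6% |
| .5 | 5.0% | >99.9% |

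At r=.3, an ICC of .4 or .8 gives 4.9% or 5.0% for the interaction. A random-intercept mixed model with THC varying by session, levels falling and a common slope gave 5.5% for the interaction and 98% for the THC effect (600 runs). With r=.3 at Session 3 and the Session 4 slope at 75%, 50%, 25% and 0% of it, the interaction has 14%, 40%, 73% and 93% power; the averaged effect has 84%, 73%, 57% and 41%.

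**The case against.** **The fallback is a different model.** The primary-analysis sentence concerns strain x time and is powered for three groups and four assessments. In the fallback strain is no longer the predictor, and nothing says THC x time decides. This stands. A reader might infer that the protocol names THC x time as primary there; it does not. The problem in that branch is conditional on carrying the interaction over.

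**The right term is already in the model.** The THC or strain effect is among the predictors, and the Hypothesis 1 text expects a main effect of strain as well as an interaction. This also stands: no term is missing, only the ranking is wrong or absent.

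**The statistical analysis plan may name the deciding term.** This answers the fallback in part. It does not answer the DEQ case, where the protocol itself names strain x time as primary for reward and states four time points that its own schedule rules out.

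**The effect may not be constant.** Fair. If it is almost gone by Session 4, the interaction can be the more powerful test. A reader might take constancy as the protocol's expectation because "the high THC group will continue to show higher blood levels than the medium THC group". That text concerns the ordering of blood levels, not the THC-outcome slope, and the same sentence expects levels to fall in all groups. Power aside, the interaction answers a question about change, whereas Hypothesis 2 is about association.

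**Titration is not the forecast.** A reader might infer that the fallback is the likely branch. The protocol mentions pilot data pointing that way, but its stated expectation is that strains separate; it raises convergence as a possibility.

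**Conclusion.** The point holds most firmly for reward by strain. There the protocol's primary test rests on two post-use sessions, its reference to four time points cannot be met, and a constant strain difference is declared significant only at about the alpha rate of 5%. That 5% follows from the algebra and does not depend on the effect size or ICC. The 68% to 99% for the main effect does depend on assumed steps of 0.3 to 0.5 SD, N=99 and ICC .6.

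For the blood-THC fallback the finding is an ambiguity with the same consequence if the interaction is taken as deciding. Working memory in the strain branch is unaffected, because its model includes pre-use sessions. The documents do not support the stronger reading that Hypothesis 2 as a whole would fail: the needed coefficient is in the model, and a fading effect would be partly detected by the interaction.

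**What to change.** In the power section and the Hypothesis 2 text:

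1. Keep the interaction with time as primary only for models that include pre-use sessions.
2. For models limited to Sessions 3-4 (DEQ by strain, and both outcomes in the blood-THC fallback), name the strain or blood-THC effect averaged over the two sessions, with time centred, as the test of Hypothesis 2. Report the interaction as secondary, describing persistence or decay.
3. Correct the statement that all four time points enter the strain branch, so that it excludes the DEQ.
4. State power for the averaged effect separately from the four-assessment figure, and label any effect size used as an assumption.

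The cost is wording and a short power statement. Visits, data and model terms stay as planned; only the coefficient named as deciding changes.

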- **Hypothesis 1.** Assuming that greater THC potency leads to greater levels of intoxication, it is hypothesized that individuals who receive the higher THC strains will demonstrate significantly greater blood THC levels. *Alternatively, it may be that individuals titrate their dose based on potency so that they achieve the same blood levels, in which case blood levels of THC should not differ between the strains.*
- **Hypothesis 2.** It is hypothesized that blood levels of THC will be positively associated with greater harm on a number of variables previously shown to be associated with THC, such as diminished working memory and increased drug reward.

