### **The impact of attrition.**

It is anticipated that some attrition will occur in this population. Based on our current pilot study and previous marijuana studies, we anticipate a 10% attrition rate between Appointment 1 baseline session and Appointment 2 the experimental session, though we have not experienced and do not anticipate differential attrition by condition. Thus, to allow for attrition, we assume a 90% retention rate over the course of data collection. To adjust for this attrition rate, we will recruit  $n\approx 111$  participants ( $n=37$  per group). Our approach to power analysis and accounting for attrition is extremely conservative, in that the techniques we will utilize in data analysis use state of the art recommendations in iterating the estimation of missing data (Schafer & Graham, 2002; Little, 1988). All analyses are intent-to-treat and all available data are utilized in analyses.

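### The .80 power at f=.12 stated for Hypotheses 1 and 2 holds only for a three-group, four-session interaction; it does not cover the two-session reward measure or the blood-THC branch of Hypothesis 2

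*Protocol*

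**What the plan says.** The section Power Analysis and Sample Size Requirement for Hypotheses 1 and 2 sets a "two-tailed alpha of .05 and power level of .80" for the primary research questions. It identifies the analysis: "The primary analysis is the test of the strain X time interaction effects across repeated assessments of THC in the blood", and extends it to working memory and the rewarding effects of the marijuana. The inputs are "three groups, four assessment points, and an average ICC = .6 between assessment points", and the result is that "a total n=99 (33 per group) will allow us to detect an interaction effect as small as" f=.12. No other power calculation or detectable effect is given.

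Hypothesis 2 is worded as an association in Objectives: "It is hypothesized that blood levels of THC will be positively associated with greater harm on a number of variables". The section Effects of THC Potency on THC Blood Levels, Working Memory, and Reward gives it two branches:

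- If strain separates blood THC, strain group is the predictor and all four time points are used.
- If participants titrate so that the groups differ little, "actual blood levels of THC will become the between-groups (continuous) independent variable in tests of Hypothesis 2", and only time points 3 and 4 are used.

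In both branches the model contains the predictor, time and their interaction. The same section defines reward by the DEQ. The instrument table in section XII (Procedures) lists the DEQ under Sessions 3 and 4 only, while the neurocognitive battery is listed at all four sessions.

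**The concern.** A reader of the power section would take it that every test under Hypotheses 1 and 2 has .80 power at f=.12. Two of those tests have a different structure from the one calculated.

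The first is reward. With the DEQ at two sessions, a four-assessment calculation cannot apply to it. Nor can the group branch of Hypothesis 2 use all four time points for this outcome.

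The second is the blood-THC branch. The predictor becomes continuous and between-person, the sessions fall from four to two, and the term that matches the wording of Hypothesis 2 is a between-person slope rather than an interaction. The assumed correlation of .6 works in opposite directions for these two kinds of effect: it raises power for a within-person interaction and lowers it for a between-person effect.

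What is at stake is how a non-significant result on reward, or on the link between THC and memory, can be described. Without its own detectable effect, such a result has only the f=.12 statement to be read against, and that statement does not apply to it.

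**Working it through.** **Inputs from the protocol.** N = 99 analysed (33 per group), α = .05, within-person correlation ρ = .6, f = .12 for the interaction. Sphericity is assumed. The attrition allowance is consistent: 99/0.90 = 110, against about 111 recruited.

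**Formulas (repeated-measures noncentral F; k groups, m sessions).**

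- Predictor-by-time interaction: λ = f²·N·m/(1 − ρ), with df (k − 1)(m − 1) and (N − k)(m − 1).
- Between-person effect: λ = f²·N·m/[1 + (m − 1)ρ], with df (k − 1) and (N − k).
- For a continuous predictor, the numerator has one degree of freedom per term and the denominator here has 97.

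**1. The protocol's own figure (k = 3, m = 4).** λ = .0144 × 99 × 4/.4 = 14.256; df 6 and 288; power **.811**. The smallest f at .80 power is .119. The printed figure reproduces.

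**2. Reward: strain by time on the DEQ (k = 3, m = 2).** λ = .0144 × 99 × 2/.4 = 7.128; df 2 and 96; power **.65** at f = .12. The smallest f at .80 power is about **.14**.

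**3. Blood-THC branch, THC by time (1 df, m = 2).** λ = .0144 × 99 × 2/.4 = 7.128; df 1 and 97; power **.75** at f = .12. The smallest f at .80 power is about **.127**.

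**4. Blood-THC branch, THC association (1 df, between-person, m = 2).** λ = f² × 99 × 2/1.6; df 1 and 97. The smallest f at .80 power is **.254**. As a per-session correlation, r = f/√(1 + f²) = .254/√1.0647 ≈ **.25**. As an illustration only, inserting f = .12 gives λ = .0144 × 99 × 2/1.6 = 1.782 and power .26.

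**Sensitivity to ρ.** The protocol fixes ρ = .6; the range .4 to .8 is an assumption made here. Each entry is power at f = .12.

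| Test | ρ = .4 | ρ = .6 | ρ = .8 |
|---|---|---|---|
| Strain × time, 4 sessions (as printed) | .61 | .81 | .99 |
| Strain × time, 2 sessions (DEQ) | .47 | .65 | .92 |
| THC × time, 2 sessions | .58 | .75 | .96 |
| THC association, 2 sessions (illustration) | .29 | .26 | .24 |

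The three interaction tests gain power as ρ rises. The association loses a little, and its smallest detectable f stays between .24 and .27 over this range.

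**The case against.** The strongest reply is that nothing printed is wrong. The power section says that the primary analysis is the strain-by-time interaction and that f=.12 refers to an interaction, and on those terms the calculation is correct. This stands: a reader might infer an arithmetic error in n=99, and there is none.

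A second reply is that f=.12 should not be carried to the association. This also stands. The protocol gives no effect size for a THC slope, and the same nominal f does not mean the same thing for a six-df interaction and a one-df slope. From the values of λ above, f=.12 corresponds to a partial eta-squared of 14.256/(14.256 + 288) = .047 in the printed design, but 1.782/(1.782 + 97) = .018 for the association. Matched at .047, power for the association would be about .58. So a reader who sees .26 beside .80 should not conclude that the study has a one-in-four chance of finding the effect it was designed for.

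Third, the model also contains THC by time, and the text does not say which term tests Hypothesis 2. On the interaction the shortfall is small (.75 against .80). That term, however, asks whether the slope changes between Times 3 and 4, whereas Hypothesis 2 is worded as an association.

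Fourth, the blood-THC branch may never be used. The protocol expects strain differences and presents titration as a possibility, although it does write of participants moderating their use to reach desired "THC levels, as our pilot data suggest". A reader might infer that this branch is the expected one; the text does not say so. It does plan for it.

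None of these replies touches the reward outcome, where the four-session calculation and the two-session DEQ schedule conflict in either branch.

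**Conclusion.** The concern holds as a mismatch of scope. The statement of .80 power at f=.12 is sound for strain by time on outcomes taken at all four sessions, such as blood THC and working memory in the group branch. It is not sound for the DEQ, where power is about .65 at f=.12 and .80 power needs f of about .14. It does not describe the blood-THC branch, where .80 power needs f of about .25 (per-session r about .25) for the association, or about .127 for THC by time.

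These values rest on 99 analysed participants, ρ = .6, sphericity, and blood THC treated as a person-level predictor, as the protocol describes it; a time-varying predictor would give different values. The detectable effect for the association needs no borrowed effect size and changes little with ρ, so it is the figure to rely on. The protocol does not say that a null slope would be taken as absence of harm. The point is only that it supplies no detectable effect against which to judge one.

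**What to change.** In the power section, restrict the .80 at f=.12 statement to the strain-by-time interaction on outcomes measured at all four sessions. Then add the detectable effects at .80 power with 99 participants and ρ = .6:

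- strain by time on the two-session DEQ: f of about .14;
- blood-THC branch, THC association over Times 3 and 4: f of about .25 (per-session r about .25);
- blood-THC branch, THC by time: f of about .127.

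In the Hypothesis 2 text, name the THC coefficient over Times 3 and 4 as the test in the blood-THC branch, because the hypothesis is worded as an association, and report it with a confidence interval. State also that DEQ models use Sessions 3 and 4 in either branch, in line with the instrument table.

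The sample size, procedures and fitted models for four-session outcomes do not change. The cost is some rewording and a less favourable stated detectable effect for reward and for the blood-THC branch.
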